5.2.2. Adverse Events (AEs)

All AEs will be coded from verbatim text to PTs and grouped by SOC using the MedDRA Version 20.1. AEs will be collected from the time of signature of informed consent throughout the treatment period and up to 30 days after the last dose of study treatment. SAEs and AESI will be collected through 90 days after the last dose of study drug. AEs are graded by investigator according to CTCAE, Version 4.03.

For the induction treatment period, TEAE analyses will include all AE’s that started on or after the first dose of study drugs and up to the date of first dose of atezolizumab in the maintenance period. If the subject did not enter the maintenance period, then AEs up to the first dose of the last cycle in the induction period + 36 days (inclusive) will be considered TEAE.

For the maintenance treatment period, TEAE analyses will include all AE's that started on or after the first dose of atezolizumab in the maintenance period through the last dose of the maintenance period + 30 days.

For TEAEs that are designated as SAEs or AESIs, data will be summarized through the last dose of atezolizumab + 90 days.

TEAEs will be summarized overall and by the period in which they occur.

Other AE variables include drug-related AEs, AEs leading to study drug discontinuation or study withdrawal, AEs leading to death, SAEs, and atezolizumab AESIs.

AEs with onset/end dates that are partially/completely missing will be imputed as follows:

(i) For onset date:

- If only the day part of the AE onset date is missing and occurs in the same month and year as the first dose date of study drug, the date of first dose of study drug will be used as the onset date of the AE. Otherwise, the first day of the month will be used to complete the onset date of the AE;
- If the day and month parts of the AE onset date are missing and occur in the same year as the first dose of study drug, the date of the first dose of study drug will be used as the onset date of the AE. Otherwise, January 1st will be used to complete the onset date of the AE;
- If the AE onset date is completely missing, the date of the first dose of study drug will be used as the onset date of the AE.

(ii) For end date:

- If only the day part of the AE end date is missing, the last day of the month will be used to complete the end date of the AE;
- If the day and month parts of the AE end date are missing, December 31st will be used to complete the end date of the AE;
- If the AE end date is completely missing and the onset date of the AE occurs after the date of the first dose of study drug, the last date during the treatment period +30 days will be used as the AE end date. If the AE end date is completely missing and the onset date of the AE occurs prior to the date of the first dose of study drug the date of the first dose of study drug will be used as the AE end date.

AEs related to hematologic toxicity will be pooled based on the preferred MedDRA Version 20.1. [Table 13](#) outlines those terms that will be consolidated.

Table 13 Preferred Terms to Be Consolidated

Presented term in the table	Preferred Term
Neutropenia	Neutropenia
	Neutrophil count decreased
Febrile neutropenia	Febrile neutropenia
Anaemia	Anaemia
	Anaemia macrocytic
	Red blood cell count decreased
	Hemoglobin decreased

Presented term in the table	Preferred Term
Thrombocytopenia	Thrombocytopenia
	Platelet count decreased
Lymphopenia	Lymphopenia
	Lymphocyte count decreased
Leukopenia	Leukopenia
	White blood cell count decreased

Infusion reaction AEs are signified in the study drug administration forms and that information is linked to the details entered on the AE page to distinguish those for a subset summary. Additionally, a summary from the AE data only will be presented for those records where “INFUSION RELATED REACTION” is a preferred term. The event terms are coded using the MedDRA Version 20.1.

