- s Peripheral blood samples will be collected at predose on Day 1 of Induction Cycle 1, Day 1 of Maintenance Cycle 1 (first cycle of maintenance part), Day 1 of Maintenance Cycle 5, and at the post-treatment visit at 90 (+7) days after the last dose of study drug.
- t Anti-atezolizumab therapeutic antibodies will be measured predose on Day 1 of Induction Cycles 1, 2, 3, and 4; Maintenance Cycles 4, 8, 12, and every eighth cycle thereafter; and at 30 (+3) and 90 (+7) days after the last dose of study drug.
- u Adverse events will be recorded from the time of informed consent. AEs will be collected through 30 days after the last dose of study drug; SAEs and AESI will be collected through 90 days after the last dose of study drug. All AEs should be followed until they are resolved, have returned to baseline, or it is deemed that further recovery is unlikely.

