#### 11.4.1. **Adverse Events, Serious Adverse Events, and Adverse Events of Special Interest**

##### 11.4.1.1. Definition of Adverse Event

An AE is defined as any untoward medical occurrence in a patient administered a medicinal product that does not necessarily have a causal relationship with this treatment. An AE can, therefore, be any unfavorable and unintended sign (including an abnormal laboratory finding), symptom, or disease temporally associated with the use of a medicinal (investigational) product, whether or not related to the study (investigational) product.

An abnormal laboratory value is not an AE unless it is considered to be clinically significant.

Adverse events include the following:

- All suspected adverse drug reactions (ADRs)
- All reactions from medication overdose, abuse, withdrawal, sensitivity, or toxicity
- Apparently unrelated illnesses, including the worsening of a pre-existing illness (see pre-existing conditions below)
- Injury or accidents (Note that if a medical condition is known to have caused the injury or accident [eg, a fall secondary to dizziness], the medical condition [dizziness] and the accident [fall] should be reported as 2 separate AEs). The outcome of the accident (eg, hip fracture secondary to the fall) should be recorded under comments.
- Abnormalities in physiological testing or physical examination (findings that require clinical intervention or further investigation beyond ordering a repeat [confirmatory] test)
- Laboratory abnormalities that are clinically significant and require clinical intervention or further investigation (beyond ordering a repeat [confirmatory] test) unless they are associated with an already reported clinical event. Laboratory abnormalities associated with a clinical event (eg, elevated liver enzymes in a patient with jaundice) should be described under comments on the report of the clinical event rather than listed as a separate AE.

An AE does not include:

- Medical or surgical procedures (eg, surgery, endoscopy, tooth extraction, transfusion); the condition that leads to the procedure will be an AE
- Pre-existing diseases or conditions present or detected at the start of the study that do not worsen
- Situations where an untoward medical occurrence has not occurred (eg, hospitalization for elective surgery, social, and/or convenience admissions)
- Overdose of either study drug or concomitant medication without any signs or symptoms
- Disease progression

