### 13.6. Safety Analyses

Summaries of safety data will be performed using the safety analysis set. Adverse event data will be coded to system organ class and preferred term using MedDRA (Version 17.1 or later). A detailed definition of treatment emergence will be provided in the SAP. The number and percentage of patients experiencing any treatment emergent AEs (TEAE) overall, and by system organ class and preferred term will be tabulated. Adverse events related to treatment will be further summarized by the treatment to which it is attributed (eg, trilaciclib, carboplatin, etoposide, or atezolizumab). Severity will be tabulated based on greatest severity observed for each patient. In analyses of grade and causality, if the same AE occurs on multiple occasions, the highest grade and strongest relationship to study drug will be summarized. Infusion-related reactions (IRRs), AEs leading to study drug discontinuation, use of concomitant medications to treat AEs, as well as incidence and severity of AEs of special interest (AESI) for atezolizumab will be tabulated separately.

Observed values and change from baseline in vital signs, ECG intervals, and hematology, clinical chemistry, urinalysis, and liver function parameters will be tabulated at each visit, as

appropriate. Toxicity grades for clinical lab parameters (eg, hematology, chemistry) will be characterized according to CTCAE, Version 4.03, when possible. Shifts in toxicity grades from baseline to each visit, and from baseline to the worst grade during the study will be summarized. Summaries examining maximum and minimum post-baseline changes will consider both scheduled and unscheduled data.

Graphical presentations of safety data will be presented as is deemed appropriate. This may include, but is not restricted to, presentation of parameters against time, concentration or shift plots. Dose modifications, interruptions, compliance, and patient exposure will be summarized for each study therapy component, where appropriate. This will include, but not limited to the following:

- Occurrence of chemotherapy delays and interruptions
- Occurrence of trilaciclib dose delays and interruptions
- Occurrence of atezolizumab dose delays and interruptions
- Relative dose intensity of carboplatin and etoposide

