5.2.4. Laboratory

Blood and urine samples for the determination of clinical chemistry, hematology, and urinalysis laboratory variables described in [Table 15](#) will be measured.

Table 15 Laboratory Assessment

Lab Category	Lab tests
Hematology	hemoglobin, white blood cell (WBC), platelet counts, ANC, ALC, Monocytes, Bands, Basophils, and Eosinophils.
Chemistry	albumin, Alkaline Phosphatase (ALP), total bilirubin, calcium, chloride, creatinine, glucose, inorganic phosphorus, potassium, total protein, Alanine Aminotransferase (ALT), Aspartate Aminotransferase (AST), Lactate Dehydrogenase (LDH), sodium, and Blood Urea Nitrogen (BUN), Lipase, Amylase, Thyrotropin, Free Thyroxine, and Free Triiodothyronine
Urinalysis	semiquantitative dipstick: specific gravity, pH, evaluation of glucose, protein, bilirubin, ketones, leukocytes, and hemoglobin microscopic examination, including RBC, WBC, and casts will be performed, if necessary

Change from baseline in laboratory test results to each assessment will be calculated. The urinalysis results will not be summarized; they will only be included in listings.

For hematology parameters, if absolute counts are not provided, they will be derived from the differential counts; the normal ranges will be left missing in those cases. The formula used will be: Differential value * Leukocyte value from the same sample.

Clinical laboratory results will be graded according to CTCAE criteria, Version 4.03 which can be found in [Table A-1](#) of Appendix. Any graded abnormality that occurs following the initiation of study drug and represents at least a 1-grade increase from the baseline assessment is defined as treatment emergent. Any assessment for which CTCAE toxicity grades are not available, will not be included in any analyses for which toxicity grades are required.

Analysis of Abnormal Hepatic Laboratory Values

The following categories of abnormal hepatic laboratory values will be evaluated for any occurrence among all post baseline assessments.

- ALT and/or AST >3x ULN, ALP < 2xULN, and Total Bilirubin > 2x ULN
- AST > 3,5,8,10, and 20x ULN, AST>5x ULN for more than 5 weeks
- ALT > 3,5,8,10, and 20x ULN, ALT > 5x ULN for more than 5 weeks
- Total Bilirubin >1.5 or >2x ULN

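### SAP 5.2.2 defines treatment-emergent adverse events, and places them in induction or maintenance, by start date alone, with no rule for an event that worsens on treatment

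*SAP*

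**What the plan says.** Protocol 13.6 leaves the definition of treatment emergence to the SAP, and Protocol 13 lets the SAP prevail where the two differ. SAP 5.2.2 is therefore the operative rule.

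- Induction: events that "started on or after the first dose of study drugs and up to the date of first dose of atezolizumab in the maintenance period". Patients who do not enter maintenance have a fixed window after the first dose of their last induction cycle.
- Maintenance: events that "started on or after the first dose of atezolizumab in the maintenance period through the last dose of the maintenance period + 30 days".
- Presentation: "TEAEs will be summarized overall and by the period in which they occur".
- Collection: "AEs will be collected from the time of signature of informed consent throughout the treatment period". Protocol Table 9-1 agrees: "Adverse events will be recorded from the time of informed consent". Its footnotes allow consent up to 28 days before the first treatment.

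SAP 6.2.8.2 builds its incidence tables (all events, serious events, atezolizumab events of special interest, fatal events, events leading to discontinuation) as categories of treatment-emergent events. For events that began before study medication, it provides only listings.

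Two other places do recognise worsening. Protocol 11.4.1.1 includes among adverse events "Apparently unrelated illnesses, including the worsening of a pre-existing illness". SAP 5.2.4 says that a graded laboratory abnormality that follows the start of study drug and "represents at least a 1-grade increase from the baseline assessment is defined as treatment emergent".

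**The concern.** Many treatment-emergence definitions have two limbs: new onset after first dose, or worsening after first dose of something already present. This SAP has only the first limb for clinical events, yet uses the second for laboratory values. Events are collected from consent, so records with a pre-dose start will exist. The eCRF items listed in Protocol 11.4.1.8 are a description, an onset date, a stop date and a grade for each event. Nothing in either document says what happens to that record when the event gets worse.

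Two things are at stake. On-treatment worsening of an event first recorded before dosing could be missing from the safety tables. The induction and maintenance tables could also misplace toxicity that became worse or serious only once atezolizumab was being given alone.

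**Working it through.** No arithmetic applies. The check is to read the rules together and follow each kind of worsening event through them.

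**Step 1. Does the treatment-emergence rule mention worsening?** No. Both period definitions in SAP 5.2.2 turn on when the event started.

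**Step 2. Does either document say how a grade increase is recorded?** No. Protocol 11.4.1.8 lists the items per event but does not say whether an increase updates the record or opens a new one. It also does not say that the recorded grade is the maximum over the event. Protocol 11.4.1.11 requires follow-up to resolution, which fits either practice.

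**Step 3. Follow three cases under each recording practice.**

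| Case | Increase kept on the existing record | Increase opens a new record |
|---|---|---|
| Illness present before consent, held as history, worsens after first dose | No earlier event record exists. The worsening is itself an adverse event (Protocol 11.4.1.1) and, if dated at worsening, is counted | Same |
| Event first recorded between consent and first dose, worsens after dosing | Start precedes first dose: not treatment-emergent, listings only | New start follows first dose: counted at its own grade |
| Event starts in induction, worsens or becomes serious in maintenance | Counted in the induction event or serious-event table, absent from maintenance | Worsened episode counted in maintenance |

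The rule works in the right-hand column and fails in two of the three rows of the middle column.

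**Step 4. Which tables are affected?** In SAP 6.2.8.2, all events and serious events are tabulated for induction, maintenance and overall; special-interest, fatal and discontinuation tables are overall only. The second case therefore affects all of these tables. The third affects the by-period event and serious-event tables, and the by-period grade and relationship tables, which cover only events related to any study drug or to atezolizumab. It does not change the overall-period tables.

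**Step 5. Does the missing-date rule help?** No. Under SAP 5.2.2, an event that began before first dose and has a completely missing end date is given the first-dose date as its end. A pre-dose event still open during treatment is thus recorded as over when treatment starts, which hides exactly the events a worsening rule would need to find.

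**The case against.** The strongest reply is that the consequences depend on a recording practice the documents leave open. If sites open a new record at each grade increase, the start-date rule gives the right answer. Completion instructions may say so; they are not among the documents. This stands, and it is why the point is conditional.

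Protocol 11.4.1.1 also handles much of the ground, since worsening of a pre-existing illness is reportable in its own right. Baseline signs and symptoms in the 4 weeks before randomization are taken as medical history (Table 9-1), and screening runs at most 14 days before first dose (Protocol 10.1), so 28 days is only the outer limit for consent. This stands too: the exposed events are those already recorded between consent and first dose, or during induction.

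Harm is also visible elsewhere. Deaths with their reasons are in the disposition table (SAP 6.2.1), overall survival counts every death (SAP 5.1.2.4), and laboratory worsening is covered by SAP 5.2.4 and the shift tables in SAP 6.2.8.3. That limits what could be lost, but it does not restore a clinical event to the serious or special-interest tables.

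The contrast with laboratory values is weaker than it looks, because those are serial measurements with a defined baseline. It shows that the SAP accepts worsening as a principle, but it is not a contradiction.

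From Protocol 13.6, "Severity will be tabulated based on greatest severity observed for each patient", a reader might infer that a maintenance-period Grade 3 or 4 is displayed under induction. That would need one record carrying the maximum grade, which is not stated, and it would reach only the by-period tables for related events.

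**Conclusion.** The definition has a real gap: treatment emergence and period assignment rest on start date only, with no worsening criterion. If grade increases stay on the existing record, two consequences follow. Events first recorded between consent and first dose that worsen on treatment leave all treatment-emergent tables. Events that start in induction and worsen or become serious in maintenance are counted in induction and missing from maintenance.

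Three stronger readings are not supported:

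- That every condition present before first dose which worsens goes uncounted. Protocol 11.4.1.1 prevents that for pre-existing illness reported with a new date.
- That the comparison between arms is biased. The rule is identical in both arms, and nothing shows a differential effect.
- That a particular number of patients is affected. The documents give no rate of pre-dose events or of their worsening, so any count would be assumption throughout and would also presume that every increase stays on one record.

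The matter is a modest one of safety reporting. It does not touch the primary endpoints, but it is worth correcting because serious and special-interest counts may be small in a trial of about 100 patients and the correction is cheap.

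**What to change.** In SAP 5.2.2:

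1. Extend both period definitions to events that started, or increased in grade, or became serious or fatal, on or after the relevant first dose.
2. Assign the period by the date of onset or of the increase, whichever made the event qualify.
3. State whether a grade increase opens a new adverse event record. If site instructions already require this, saying so largely closes the point.
4. Where records were not split and the increase cannot be dated, count a pre-dose event that is ongoing at first dose as treatment-emergent if its recorded grade, seriousness, outcome or action taken shows worsening after dosing. This fallback is needed because grade-change dates are not among the listed eCRF items and the trial was already collecting data when the plan was amended.
5. Change the missing end-date rule so that an ongoing pre-dose event is not ended on the first-dose date.

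The cost is a few sentences in the SAP, with some extra records, queries and programming. Instructing sites to split records helps only from that time on; earlier records would rely on queries or the fallback.

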5.2.3. Vital Signs

Vital signs include pulse rate, respiratory rate, systolic blood pressure (SBP), diastolic blood pressure (DBP), weight, height (only measured at screening), body temperature and oxygen saturation. Body Mass Index (BMI) will be computed as $\text{weight (kg)} / [\text{height (m)}]^2$, Body Surface Area (BSA) will be computed using DuBois-DuBois formula as $0.20247 \times [\text{height (m)}]^{0.725} \times [\text{weight (kg)}]^{0.425}$.

For vital signs, change from baseline to each post-baseline visit and timepoint will be calculated. Vitals will be summarized by visit as collected and not windowed.

The potentially clinically significant findings of vital signs will also be defined based on criteria defined in [Table 14](#):

Table 14 Potentially Clinically Significant Criteria for Vital Signs

Vital Sign Parameter	Criterion value	Change from baseline
SBP	≥ 180 mmHg	Increase ≥ 40 mmHg
	≤ 90 mmHg	Decrease ≥ 40 mmHg
DBP	≥ 105 mmHg	Increase ≥ 20 mmHg
	≤ 50 mmHg	Decrease ≥ 20 mmHg
Oxygen Saturation	$\leq 90\%$	n/a
Pulse	≥ 120 bpm	Increase ≥ 40 bpm
	≤ 50 bpm	Decrease ≥ 40 bpm
Weight	n/a	Change $\geq 10\%$

bpm = beats per minute

5.2.4. Laboratory

Blood and urine samples for the determination of clinical chemistry, hematology, and urinalysis laboratory variables described in [Table 15](#) will be measured.

Table 15 Laboratory Assessment

Lab Category	Lab tests
Hematology	hemoglobin, white blood cell (WBC), platelet counts, ANC, ALC, Monocytes, Bands, Basophils, and Eosinophils.
Chemistry	albumin, Alkaline Phosphatase (ALP), total bilirubin, calcium, chloride, creatinine, glucose, inorganic phosphorus, potassium, total protein, Alanine Aminotransferase (ALT), Aspartate Aminotransferase (AST), Lactate Dehydrogenase (LDH), sodium, and Blood Urea Nitrogen (BUN), Lipase, Amylase, Thyrotropin, Free Thyroxine, and Free Triiodothyronine
Urinalysis	semiquantitative dipstick: specific gravity, pH, evaluation of glucose, protein, bilirubin, ketones, leukocytes, and hemoglobin microscopic examination, including RBC, WBC, and casts will be performed, if necessary

Change from baseline in laboratory test results to each assessment will be calculated. The urinalysis results will not be summarized; they will only be included in listings.

For hematology parameters, if absolute counts are not provided, they will be derived from the differential counts; the normal ranges will be left missing in those cases. The formula used will be: Differential value * Leukocyte value from the same sample.

Clinical laboratory results will be graded according to CTCAE criteria, Version 4.03 which can be found in [Table A-1](#) of Appendix. Any graded abnormality that occurs following the initiation of study drug and represents at least a 1-grade increase from the baseline assessment is defined as treatment emergent. Any assessment for which CTCAE toxicity grades are not available, will not be included in any analyses for which toxicity grades are required.

Analysis of Abnormal Hepatic Laboratory Values

The following categories of abnormal hepatic laboratory values will be evaluated for any occurrence among all post baseline assessments.

- ALT and/or AST >3x ULN, ALP < 2xULN, and Total Bilirubin > 2x ULN
- AST > 3,5,8,10, and 20x ULN, AST>5x ULN for more than 5 weeks
- ALT > 3,5,8,10, and 20x ULN, ALT > 5x ULN for more than 5 weeks
- Total Bilirubin >1.5 or >2x ULN

